o Patients with fibromyalgia
o Patients with mental disorders

Elimination criteria:

- o Patients who do not wish to continue with electrostimulation therapies and / or the use of a splint.
- o Patients who, during TMD treatment, require dental restorations or root canals.
- o Patients who during TMD treatment suffer from some type of dental trauma or fracture.

Control group selection

The randomization of the total sample (84 patients) will be carried out to obtain the three study groups (28 patients per group) including the control group (CG = Occlusal splint).

Variables (identification, definition, measurement scale)

Sociodemographic variables		
Variable	Operational Definition	Measurement scale
Age	Years completed that the person indicates to have when making the medical history. ➤ Information obtained from the medical history	Number of years completed
Gender	Gender to which the person indicated in the medical history belongs. ➤ Observed during the medical history	1. Female 2. Male
Clinical variables		
Variable	Operational Definition	Measurement scale
Temporomandibular dysfunction (DTM)	Functional alteration of the temporomandibular joint that is identified by the presence of muscle or joint pain, joint sounds and restriction, deviation or deflection in the mandibular opening.	1. Muscle 2. Disc displacement 3. Arthralgia, arthritis, osteoarthritis
Body mass index (BMI)	Measure of obesity, where the mass is expressed in kilograms, and is divided by the square of the height in meters categorically determined based on the classification of nutritional status of the World Health Organization (WHO, 1990) ➤ Measurement estimated by measuring weight and height during clinical evaluation.	1. Under weight 2. Overweight 3. Obesity
Systemic diseases	Diagnosed systemic alteration that the patient responds to the question "Do you have any systemic disease?" when making the medical history. ➤ Information obtained from the medical history	1. Diabetes 2. Arterial hypertension 3. Rheumatoid arthritis 4. Diabetes and Hypertension
Drug intake	Taking medications prescribed by medical indication for some type of systemic alteration. ➤ Information obtained from the medical history	1. Not 2. Yes
Use of prosthetics	Use or presence of removable oral prosthesis at the time of clinical evaluation. ➤ Information obtained when conducting the clinical evaluation	1. Total upper arch prosthesis 2. Total lower arch prosthesis 3. Total prosthesis both arches 4. Removable partial upper arch prosthesis 5. Removable lower arch partial denture 6. Removable partial denture both arches

Number of teeth present	Number of teeth present in the mouth at the time of the clinical examination ➤ Information obtained when conducting the clinical evaluation	
 1. 1 to 8 teeth 2. 9 to 16 teeth 3. 17 to 24 teeth 4. 25 to 32 teeth
DTM Treatment	Type of therapy that the patient receives for 6 weeks for the treatment of DTM.	
 1. Transcutaneous electrostimulation therapy and occlusal splint 2. Percutaneous electrostimulation therapy and occlusal splint 3. Occlusal splint

Variables of signs and symptoms of DTM		
Variable	Definición operacional	Escala de medición
Muscle pain	Amount of muscular pain reported by the patient when applying a pressure of 1.5 Kg / cm ² in masseter muscles and 2.4 Kg / cm ² in temporal muscles using a circular tip of a Baseline brand pressure algometer. (52) ➤ Information obtained with visual analog scale when conducting the clinical evaluation.	0 to 10 Where 0 represents the absence of perceived pain, and 10 the maximum amount of pain
Joint pain	Amount of joint pain reported by the patient when applying a pressure of 1.5 Kg / cm ² to the surface area of the ATM using a circular tip of a baseline pressure algometer. (52) ➤ Information obtained with visual analog scale when conducting the clinical evaluation.	0 to 10 Where 0 represents the absence of perceived pain, and 10 the maximum amount of pain
Limitation of mouth opening	Amount of millimeters measured from the incisal edge of the upper anterior teeth to the incisal edge of the lower anterior teeth with a TeraBite ruler. ➤ Information obtained when conducting the clinical evaluation	Millimeters (mm) 
 1. Normal opening (> 40mm) 2. Opening limitation (<40mm.)
Presence of joint noises	Sound detected and recorded by the operator using a stethoscope placed in the anterior atrial area above the TMJ when making mandibular opening and closing movements. ➤ Information obtained when conducting the clinical evaluation	
 1) Not 2) Yes

Heart rate	Number of times the heart beats for one minute, measured with using a finger oximeter Pulox Oxímetro de Pulso PO-200	Number of beats
	Information obtained when conducting the clinical evaluation	Norm (60-100 beats)

Information gathering methods (selection of sources, methods, techniques and procedures):

Convenience samplings will be carried out, based on the evaluation of the clinical history, radiological studies (orthopantomography and comparative radiography of the TMJ open and closed mouth) and clinical examination, in patients of the Physiology Laboratory of the DEPeI UNAM, who will be admitted during the period from August to December 2020.

The diagnostic process of Temporomandibular Dysfunction (TMD) will be carried out by the Principal Investigator (Doctoral Student of the Master's and Doctoral Program in

Medical, Dental and Health Sciences) in patients who come to request service from the

Laboratory of Physiology of the Division of Postgraduate Studies and Research (DEPeI) of the School of Dentistry UNAM (UNAM) during the period from August to December 2020. Mtra. [name] (Principal Investigator) carried out the calibration process for the diagnosis of temporomandibular disorders based on the diagnostic criteria of the American Dental Association, under the mentorship of Doctor [name] at the Laboratory of Physiology of Dentistry of the University of the Republic, Uruguay. (Annexed 2)

The use of diagnostic criteria for the investigation of temporomandibular disorders (CDI / TMD) will be used (54). The instrument allows a physical examination and medical history in two axes. Axis I, based on a clinical examination divided into: a) muscular disorders b) disc displacements and, c) arthralgia, arthritis, osteoarthritis. The second axis comprises a questionnaire based on disabilities due to chronic pain and psychological aspects. (fifty)

Once the diagnosis is made, a protocolized algorithm is used for CDI / TMD scores (axis I and axis II) and thus determine the Diagnostic classification of TMD. (1.- muscular TMD, 2.- joint TMD, 3.- inflammatory TMD) (50)

After the diagnosis of TMD, a general clinical evaluation will be carried out to establish whether they meet the inclusion criteria, all patients who meet the characteristics described and who wish to participate in the study will sign an informed consent. After being included, a general, regional and local clinical examination will be carried out to collect baseline data for the study variables.

Data collection will be by primary technique and direct method through interviews (series of questions asked during the anamnesis for the complete record of the clinical history), observation (dental clinical evaluation) and digital surface electromyography, all carried out in a chair. at the DEPeI Physiology Laboratory, UNAM. This procedure will be performed by a previously trained and

standardized examiner and annotator (Cohen's Kappa 0.7), for a clearer performance of the clinical examination and the reduction of bias by the examiner for clinical methods. For the clinical examination, it will be performed in clockwise order, starting with the upper right quadrant. The first review will correspond to the presence of mixed dentition, use of prostheses, number of teeth, muscle pain (with a pressure algometer applying 1.5 kg / cm² in masseter muscles, and 2.4 kg / cm² in temporal muscles), joint pain (with algometer pressure applying 1.5 kg / cm²), presence of noises, limitation to mouth opening (with Terabite) and heart rate.

To assess pain by means of muscle and joint palpation with an algometer, the patient will be seated in a relaxed position, the evaluator will place the fine circular surface of the algometer perpendicular to the skin and an increasing pressure of 0.5 kg / cm² will be applied increasing gradually over one minute until reaching 1.5 kg / cm².

The patient will be instructed to verbalize the moment when pressure was exerted if a painful sensation was caused by muscle and in the joint area.

The treatment for TMD will be carried out by means of the conventional treatment with an occlusal splint and as an auxiliary method, transcutaneous and percutaneous electrostimulation therapies will be applied by the same operator during the period from August 2020 to June 2021. The appointments for clinical control for signs and symptoms of TMD, splint adjustment, electromyographic records and application of electrostimulation therapy as an adjunct to the use of splint, will be scheduled once a week in the Physiology Laboratory from 9:00 am to 1:00 pm and from 2:00 pm to 6:00 pm: 00pm for six consecutive weeks.

• **Electromyographic recording technique**

The registration system (hardware and software) that will be used for the electromyographic evaluation is the Electromyograph 1.2 UNAM-CINVESTAV, which consists of a two-channel system for the analysis of the electromyographic signal that offers greater precision and facilitates muscle assessment through the estimation made by the software of the RMS for its acronym in English (Root Mean Square) and Hurts Index. (53)

The RMS and Hurts Index will be recorded using three electrodes: one placed at the muscular origin, another at the insertion, and finally one in the behind-the-ear area as a ground or neutral electrode. The RMS recording is performed at maximum intercuspation for 30 seconds; the action potential that is expressed in electrical energy will be recorded in microvolts per second ($\mu\text{V} / \text{s}$).

6 electromyographic recordings will be performed on each patient (one record each week) during the time of splint use. Electromyographic recordings will be scheduled as well as follow-up control appointments, to make adjustments to the physiological occlusal splint.

Occlusal splint fabrication technique

The occlusal splints for the treatment of TMD will be the same for all the participants, they will be made by the Principal Investigator in the Physiology Laboratory of DEPeI, UNAM. The indications for the use of a splint and hygiene will be the same in all patients (the splint is worn 24 hours a day, it is

removed for eating and brushing teeth). The splint is washed with neutral liquid hand soap, no brushing or scrubbing).

To make the occlusal splint, an impression of the maxillary dental arches will be taken with alginate; the positive will be obtained with type IV stone plaster. Once the plaster has set, the models will be obtained to make the splint with a thermoplastic vacuum machine. A .060 "acetate sheet will be placed, and the second acetate will be a .080" caliber. Once the acetate sheet has been adapted to the working model, it will be cut with a carbide disk on the design previously made on the plaster model, marking the middle part of all the upper teeth on the buccal part to have the guide cutting. Surpluses will be removed with the help of a bur and polished to avoid damage to the soft tissues with a blanket wheel. Once this is done, he will test the patient to check that it does not generate any discomfort. Later it will be adjusted again to the working model to carry out the relining.

Relining is done with self-curing acrylic on the occlusal surface of the splint, leveling the amount of material on a glass tile. Then the occlusal adjustment is made with the help of articulating paper and thus achieve a homogeneous occlusal bite. Excess acrylic will be removed and placed back in the mouth to verify the dimension of the splint (interdental unocclusion), taking care that it does not interfere with any mandibular movement. It is finished by polishing the splint with the help of a blanket wheel and polyacril.

Transcutaneous electrical stimulation technique

The transcutaneous electrostimulation therapies will be carried out by the Principal Investigator, who will be trained in the ISSSTE Clinic Specialties East Leonardo Bravo Complex in the acupuncture service under the supervision of [name] [name]. (Surgeon, Specialist in Family Medicine. Training in acupuncture in different institutions. Master's in Medical Education, Doctorate in Education, Professor of various courses in acupuncture from a medical perspective. Academic of the Faculty of Medicine of UNAM.)

For transcutaneous electro stimulation therapy, Kendall® MediTrace 100 conductive adhesive ECG electrodes (pediatric) with a diameter of 2.4 cm, and portable electro-stimulator equipment KWD-808 (professional equipment for electroacupuncture and rehabilitation) will be used.

The patient will be positioned on the dental chair, the superficial area of the skin of the masseter muscle will be cleaned with alcohol and cotton. Two Kendall® MediTrace 100 electrodes will be placed in each masseter muscle (right and left), considering the same references that were used for the electrodes placed for the electromyographic recording; the first electrode is placed at the origin of the masseter muscle or superficial area of the mandibular condyle and the second at the insertion of the masseter muscle at the angle of the mandible. After placing the electrodes, the KWD-808 electroacupuncture device will be connected to the patient by means of two double alligator cables; the alligators will be pressed to the metal head of each electrode: the positive pole (red color) will be connected at the origin of the masseter muscle and the negative pole (black color) at the insertion of the masseter muscle.

Before nerve stimulation, all patients will be informed of the perceived sensation, which in some patients will range from imperceptible to barely noticeable or not very noticeable.

The parameters to be used will be: pulse duration until sensory activation and high intensities, but with an established limit to prevent muscle contraction and that allows maximum comfort for 20 minutes. Current will be transmitted with square or rectangular waveform, the stimulation frequency: two frequency bands (low: 210Hz and high 10140Hz.); wave amplitude: 3050 volts, pulse duration: 40100 msec; and the output intensity: 0.70 (for 100Hz). The treatment time will be 20 minutes; the equipment has the quality of timing itself and after time it will stop transmitting a signal to the patient. The treatment will consist of the application of six consecutive therapies programs weekly.

Percutaneous electrical stimulation technique

The transcutaneous electrostimulation therapies will be carried out by the Principal Investigator, who will be trained in the ISSSTE Clinic Specialties East Leonardo Bravo Complex in the acupuncture service under the supervision of [name] [name]. (Surgeon, Specialist in Family Medicine. Training in acupuncture in different institutions. Master's in Medical Education, Doctorate in Education, Professor of various courses in acupuncture from a medical perspective. Academic of the Faculty of Medicine of UNAM.)

For percutaneous electrostimulation therapies, sterile steel acupuncture needles of 0.25x13mm, disposable AcuBEST brand (FDA 510K), and portable electrostimulator equipment KWD-808 (professional equipment for electroacupuncture and rehabilitation) will be used.

Prior to the placement of therapy, the superficial area of the skin of the masseter muscle will be cleaned with alcohol and cotton. The puncture technique will be carried out by taking the needle through the body (not by the handle), the lower part is held between the thumb and index finger of the right hand, allowing the tip of the needle to pass. Directing the needle to the acupuncture point to insert it quickly (penetrating 5 mm).

Two needles will be placed in the right masseter muscle and two in the left masseter muscle each at the reference trigger points (local TMD points), following the

"Practical recommendations for the treatment of Temporomandibular Disorders" (55); the area to be punctured is the origin of the masseter muscle or superficial area of the mandibular condyle anterior to the atrial tragus approximately 1cm away (proximal acupuncture points: Gb3, Si 19, Gb 2, St 7), insertion of the masseter muscle at the angle of the mandible (Proximal acupuncture points: St6, St5). For this study, distal stitches will not be placed.

After placing the needles, the KWD-808 electroacupuncture device will be connected to the patient; The two double alligator cables will be connected to each patient by means of the alligators that will directly press the head of the needles. The positive pole (red color) will be connected at the origin of the masseter muscle and the negative pole (black color) will be placed at the insertion of the masseter muscle.

Before nerve stimulation, all patients will be informed of the perceived sensation, which in some patients will range from imperceptible to barely noticeable or not very noticeable.

The parameters to be used will be: pulse duration until sensory activation and high intensities, but with an established limit to prevent muscle contraction and that allows maximum comfort for 20 minutes. Current will be transmitted with square or rectangular waveform, the stimulation frequency: two frequency bands (low: 210Hz and high 10140Hz.); wave amplitude: 3050 volts, pulse duration: 40100 msec; and the output intensity: 0.70 (for 100Hz). The treatment time will be 20 minutes: The equipment has the quality of timing itself and after time it will stop transmitting a signal to the patient.

The treatment will be carried out every week with a total of six continuous therapies or if the patient deserves it until the remission of symptoms.

Pilot test

A pilot test of transcutaneous and percutaneous electrical stimulation therapies will be carried out in a selection of 8 patients who wish to participate in the study at the DEPeI Physiology Laboratory. The appropriate placement of the points to be stimulated during therapy, the patient preparation time for therapy, the clinical examination to collect the independent variables, and the electromyographic recording method will be identified.

The electromyography will identify the RMS and Hurts Index values of each recording and the changes in the electrical activity of the masseter muscles will be evaluated during electrostimulation and splint appointments. The criteria for the electromyographic recording method and its duration (30 seconds, measured in microvolts (μV)) will be evaluated.

Processing record methods

The registration of data processing will be carried out in two stages:

- During the first stage, the information obtained with respect to the variables of interest will be recorded in the Clinical History of the Physiology Laboratory of each patient, which will be filled out during the clinical evaluation, electrostimulation therapies and electromyographic record in maximum intercuspation.
- In the second stage, the database will be created, transferring the data recorded in the Information Collection Instruments format for each patient to an Excel spreadsheet, to later perform the statistical analysis in the statistical software Stata version 14.

Statistical data analysis plan

o A descriptive analysis of the main clinical characteristics of the population studied will be carried out in the case of continuous variables, the mean and standard deviation or the median and its interquartile range will be reported according to its distribution normal and antagonistic as n and percentage (%).

o The muscle effect of electrostimulation therapies within and between groups over time (before and during the 6 weeks of treatment), will be calculated using two-way ANOVA for repeated measures. Furthermore, the significant effect size of the comparison is calculated according to Cohen's effects (small (0.20), moderate (0.50) and large (0.80)).

o To identify the changes in the electromyographic activity of the multifractal analysis (Hurts Index and RMS) recorded by time of the right and left masseter muscles of all subjects, since each subject will be evaluated in 6 instances weekly, multilevel models will be adjusted (56) to describe the effect of the passage of time (T0 = Baseline, T1 = 7 days, T2 = 14 days, T3 = 21 days, T4 = 28 days, T5 = 35 days,

T6 = 42 days) of splint use and electrostimulation therapy and the effect of different explanatory variables on this change as on the initial value.

o All statistical calculations will be carried out in Stata 14 software (StataCorp., 2015).

Organization

a) Human resources

Tutor: [name] [name]

Tutorial Committee: Dra. [name] and [name] [name]

Operator: Mtra. [name]

External advisors: [name] and [name] [name]

b) Material resources:

EQUIPOS	INSTRUMENTAL	MATERIAL	STATIONERY
(1) Unidad odontológica	(10) Diagnostic equipment (mirror, caliper, scanner)	(50) (25 packs) Kendall® Electrodes	(50) Medical record formats -
(1) Electroestimulador de presión "Baseline" (1)	(3) Therbite	(50) (10 packs) Acupoint® needles	Laboratory of Physiology
Electromiógrafo digital CINVESTAV-UNAM	(2) Algometer	0.025mm x 25mm	(50) Informed consent forms
(1) Electroestimulador KWD-808	(100) Slay Tongues	(65) (2 boxes) Manhole covers	(50) Data collection sheets
(1) Computadora		(4 boxes) Gloves (5) Aerosol disinfectant	
(1) Impresora		(3 packs) Gauze	
(1) Cámara fotográfica		(1) Alcohol	
		(2 packs) Cotton	

c) Research development stages:

I. Training stage:

During the first, a review of the literature will be carried out and the methods of applying the therapies will be described.

The training process for the application of electrostimulation therapies will be completed based on the WHO Guidelines established in the Official Mexican NOM-172-SSA1-1998, which specifies the operating criteria for the practice of human acupuncture and related methods (electrostimulation therapies). The Standard governs that the training of a Physician or Health Personnel to fully exercise these therapies requires training of at least 350 academic hours. For this reason, the main researcher will complete during this stage the theoretical, practical and clinical preparation course taught by the UNAM Faculty of Medicine "Diploma in Complementary Medicine and

Acupuncture" with a total of 450 academic hours lasting one year (August 2019-September 2020), to comply with the basic training and training guidelines for the application of electrostimulation therapies.

The pilot test of transcutaneous and percutaneous electrostimulation therapies will be carried out in 8 patients from the Physiology Laboratory.

The recruitment phase of the sample will be carried out by evaluating the patients, the TMD diagnostic process and the evaluation of inclusion criteria who attend the Physiology Laboratory of the DEPEL UNAM during the period from August to December 2020. The randomization will be carried out of patients recruited during this period.

II. Clinical stage

The sociodemographic, clinical, signs and symptoms of TMD and neuromuscular variables of the patients will be measured and recorded.

Occlusal splints will be made to start with TMD treatments

Transcutaneous and percutaneous electrostimulation therapies will be applied

Scheduled electromyographic recordings will be performed weekly for a period of 6 weeks.

III. Results analysis stage

The database and statistical analysis of the results will be carried out

Knowledge dissemination exercises (Article writing)

BUDGET

PAPIIT IT201320 project

a) Ethical aspects:

In accordance with article 17 of the regulation of the General Health Law on Health Research (SS) in its second title, this project is considered Research with a risk greater than the minimum: since they are considered: radiological studies and with microwaves and modalities that are defined in article 65 of these Regulations, trials with new devices, procedures that use random methods of assignment to therapeutic schemes, for which the signing of informed consent will be essential.

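### Joint noise is recorded by the operator, the protocol's term for the person giving the stimulation, and no outcome assessor is masked or stated to be separate from the therapist

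*Protocol*

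**What the plan says.** All references are to the Protocol.

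- **Who treats.** Information gathering methods: "transcutaneous and percutaneous electrostimulation therapies will be applied by the same operator". The transcutaneous technique section adds "The transcutaneous electrostimulation therapies will be carried out by the Principal Investigator", and the percutaneous section repeats that sentence, still with the word transcutaneous. The Organization section lists one operator, with the same academic title that the information-gathering section gives the Principal Investigator.
- **Who scores joint noise.** Table of signs and symptoms: "Sound detected and recorded by the operator using a stethoscope placed in the anterior atrial area above the TMJ", scored no or yes. The Specific objectives compare joint sounds between the three groups.
- **Who collects data.** Information gathering methods describes interview, clinical examination and surface electromyography, done by a trained "standardized examiner and annotator (Cohen's Kappa 0.7"). The stated purpose includes reducing examiner bias. Noises are on that examination list. For pain, an evaluator applies the algometer and the score is a patient-reported 0 to 10 VAS.
- **How EMG is taken.** Electromyographic recording technique: "The RMS recording is performed at maximum intercuspation for 30 seconds". Software estimates RMS and the Hurst index. That section does not say who places the electrodes or gives the instruction.
- **When.** Control of signs and symptoms, splint adjustment, EMG and stimulation are booked together once a week. The order within the visit is not stated.

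**The concern.** The person who applies needles or surface electrodes necessarily knows the arm, and the Hypothesis section predicts that the percutaneous arm will do best. If that person also decides whether a joint noise is present, expectation can enter the outcome directly.

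Two other measurements are exposed less directly. Pain is reported by the patient, but under pressure that an evaluator raises by hand. RMS is calculated by software, but from a voluntary maximal clench that depends on the instruction, the encouragement and the electrode placement.

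At stake is whether a difference between groups reflects treatment or measurement. A bias that differs by arm at the time of recording cannot be removed at analysis.

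**Working it through.** The point rests on reading the sections together. No figure in the plan has to be reproduced.

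**Roles side by side**

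| Task | Role named | Section |
|---|---|---|
| Both stimulation therapies | the same operator; Principal Investigator | Information gathering methods; technique sections |
| Joint noise | operator | Table of signs and symptoms |
| Joint noise, within the clinical examination | examiner and annotator | Information gathering methods |
| Algometer pressure | evaluator | Information gathering methods |
| Electromyography | examiner and annotator | Information gathering methods |
| Electrode placement and clench instruction | nobody named | Electromyographic recording technique |

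1. Joint noise has two named roles, and one of them is the term used for the therapist.
2. The examiner and annotator are described as trained and standardized. They are not described as masked, or as different people from the operator. A kappa of 0.7 measures agreement between raters. It does not show masking and does not bound a bias that differs by arm.
3. The examiner paragraph follows directly on the collection of baseline data. The description of the weekly appointments names no assessor.
4. No sham procedure is described for the splint-only arm, and outcome checks share the visit with stimulation. An assessor present during the session would see the arm.

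**Illustration for RMS (shifts assumed, not documented)**

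Inputs from the Sample size calculation: within-group mean square 74.2155, so SD = √74.2155 = 8.615 µV; 25 patients per group; group means 90.205, 79.99 and 81.27, so the planning mean is 251.465/3 = 83.8 µV. Assume no true effect and a constant shift b in one arm of a two-sided 5% t-test with 48 df:

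non-centrality = (b/8.615)/√(2/25)

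| b (µV) | % of 83.8 | Non-centrality | False-positive rate |
|---|---|---|---|
| 1 | 1.2 | 0.41 | 0.069 |
| 2 | 2.4 | 0.82 | 0.127 |
| 3 | 3.6 | 1.23 | 0.226 |
| 4 | 4.8 | 1.64 | 0.363 |

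The result is sensitive to the SD. The group variances printed in the plan run from 24.78 (SD 4.98) to 168.56 (SD 12.98). At b = 2 µV they give about 28% and 8% respectively. The variances come from four trapezius values per group. The test is a single pairwise comparison, whereas the plan calls for repeated-measures ANOVA and multilevel models.

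**The case against.** The strongest reply has five parts.

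- **One operator for both therapies is not a fault.** It removes therapist differences between the two stimulation arms and says nothing in itself about measurement. This stands. The problem appears only when that sentence is read with the joint-noise definition.
- **Only joint noise is tied to the operator.** This also stands. A reader might infer that the therapist records all the outcome signs, but the documents do not say so: pain is patient-reported under an evaluator, the EMG is given to the examiner, and nobody is named specifically for mouth opening or heart rate. Operator in the table might also mean simply whoever holds the stethoscope, but the wording leaves that open.
- **Examiner and operator may be one person.** The names are removed, and the Organization section lists an operator but no examiner. If so, the two sections do not conflict, and changing one word does not create masking. That is a fair limit on the remedy. It confirms the underlying weakness, because the therapist would then be doing all the measuring.
- **RMS and the Hurst index are software output.** Any effect on them is indirect. Coding the files afterwards would add little, because it cannot undo a biased recording.
- **The false-positive figures show no actual bias.** Correct. The arithmetic applies to a shift from any source. A reader might infer that the trial's error rate is 13% or more, or that the results must favour stimulation or the percutaneous arm. The documents support neither; the direction is only a plausible inference from the stated hypothesis.

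**Conclusion.** The point holds in a limited form. Two sections name different roles for scoring joint noise, one of them the protocol's term for the therapist. The protocol as shown does not mask any assessor or separate the examiner from the therapist.

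The risk is direct for joint noise, a secondary between-group outcome. It is indirect for pain under the algometer and for EMG at maximal clench. Neither size nor direction is documented, and the RMS figures only show how sensitive a comparison would be to small shifts, under the planning SD, 25 per arm and no true effect.

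Who measures, and with what knowledge of the arm, belongs in the protocol and has to be settled before recruitment. The change should be made, but the documents do not show that the main outcomes are compromised.

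**What to change.** 1. Reconcile the joint-noise definition, the examiner paragraph and the description of the weekly appointments. In the joint-noise definition, replace the operator with the examiner.
2. State that the examiner and annotator already provided for take all signs, symptoms and EMG at every scheduled assessment from T0 to T6, before that day's stimulation. Where they are not the treating operator, state that they have no access to the allocation.
3. Use one scripted clench instruction in all three arms, and have the patient mark the VAS sheet.
4. If examiner and operator are the same person, keep the scripted instruction, the patient-marked VAS and measurement before stimulation, and state plainly that assessment was unmasked.

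**Cost.** Protocol wording, a script and some scheduling effort, because measurement must come before therapy within a shared appointment. No new staff are needed for items 1, 3 and 4. Item 2 gives real masking only if the examiner is not the therapist. Patients stay unmasked, so their own expectation can still affect the clench and the pain score.
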